## 1.0 TRIAL SUMMARY

Title:	Phase II study of Pembrolizumab and Itacitinib (INCB039110) for First Line Treatment of Metastatic Non-Small Cell Lung Cancer Expressing PD-L1
Abbreviated Title	Pembrolizumab and itacitinib (INCB039110) for NSCLC
Protocol Numbers	UPCC#09517; IRB#828910; NCT03425006; IND#137721
Trial Phase	Phase II
Study Center(s)	University of Pennsylvania
Study Population	The first line treatment of patients with metastatic PD-L1 positive non-small cell lung cancer (NSCLC)
Methodology	This is a single center, single arm phase 2 study to establish the safety and efficacy of itacitinib (also known as INCB039110) administered in combination with pembrolizumab in patients with metastatic PD-L1 positive non-small cell lung cancer (NSCLC).
Study Drugs, Dose and Regimen	
Study Drug(s)
 

• Itacitinib: a JAK 1 selective small molecule inhibitor; an investigational agent that is study supplied

• Pembrolizumab: a highly selective humanized monoclonal antibody (mAb)

 
Dose and Route of Administration
 

• Itacitinib: 200mg PO (extended release formulation)

• Pembrolizumab: 200mg IV infusion over 30 minutes

 
Regimen
 

• Treatment = 3 week (Q3W) dosing cycles

• Itacitinib: Once daily for Cycle 3 and Cycle 4 (up to 6 weeks)

• Pembrolizumab: Q3 week cycles of treatment beginning at Day 1; if the PI considers it beneficial for the subject, a fifth cycle may be administered prior to EOS visit.

Number of trial subjects	Up to 48 evaluable subjects
Estimated duration of trial	Approximately 48 months

CONFIDENTIAL

This material is the property of the University of Pennsylvania. Do not disclose or use except as authorized in writing by the study sponsor.

## 2.0 TRIAL DESIGN

### 2.1 *Trial Design*

This is an optimal 3-stage Phase II trial of pembrolizumab and itacitinib for first line treatment of PD-L1 positive metastatic NSCLC. Up to 48 evaluable subjects will be enrolled to examine the efficacy of adding itacitinib to pembrolizumab among patients with previously untreated metastatic NSCLC with tumor PD-L1 expression greater than or equal to 50%. Subjects will receive 2 cycles of pembrolizumab (200mg every 3 weeks), and then undergo repeat imaging and tumor biopsy. Beginning on the Day 1 of Cycle 3 the subject will receive itacitinib (selective JAK1 inhibitor) 200 mg daily for 6 weeks. Pembrolizumab will be continued at the same dose and frequency. After 6 weeks of treatment (week 12 of treatment overall) with itacitinib, repeat imaging and tumor biopsy will be performed. The scan is purely for biopsy planning, and no treatment decisions will be made based upon the results ([Figure 1](#)). Objective response by RECIST 1.1 will be determined based on the week 12 scan. Subjects who either experience documented progressive disease during the first 12 weeks of treatment or complete the first 12 weeks of treatment and undergo re-staging (i.e., PET/CT scan) will be considered evaluable for objective response evaluation. Subjects who are withdrawn from study (due to toxicity or other reasons) in the first 12 weeks of treatment and who do not undergo re-staging will be considered unevaluable for objective response evaluation but will be included in the safety analyses. These subjects will be replaced. Objective response rate (ORR) is defined as the proportion of evaluable subjects who achieve a complete or partial response according to RECIST 1.1 criteria.

The ORR for pembrolizumab in untreated PD-L1 positive advanced NSCLC was recently reported to be 45% (95% CI 37-53%) [1]. The 3-stage optimal design tests the null hypothesis that the  $ORR \leq 35\%$  (clearly inferior to pembrolizumab) versus the alternative that the  $ORR \geq 55\%$  (clearly superior to pembrolizumab) [2]. Eleven evaluable subjects will be entered into the first stage of the study. If 2 or fewer of these 11 subjects respond, then the trial will be terminated. If at least 3 of these subjects respond, then an additional 19 evaluable subjects will be entered into the second stage of the study. If 12 or fewer of these 30 subjects respond, then the trial will be terminated. If at least 13 of these subjects respond, then an additional 18 evaluable subjects will be entered into the third stage of the study. If 20 or fewer of these 48 subjects respond, then it will be concluded that the regimen does not merit further investigation. If at least 21 of these 48 subjects respond, then it will be concluded that the regimen merits further investigation. If the true objective response rate is 35%, then the probability of recommending the regimen for further investigation (false positive error), is 0.100. If the true objective response rate is 55%, then the probability of recommending the regimen for further investigation (power), is 0.906. If the true objective response rate is 35%, then the probability of early termination of the trial by the end of the second stage is 0.786. The software program, PASS v14 was employed to define this 3-stage design.

As of Protocol Amendment V5, subjects will continue on study treatment for up to 12 weeks (4 treatment cycles), followed by an End of Study Visit (EOS) at Week 16. If the PI considers it beneficial to the subject, a fifth cycle may be administered prior to the EOS visit. Subjects who remained on study treatment beyond Week 16 prior to the approval of Protocol Amendment V5, will be asked to undergo an End of Study Visit at their next clinic appointment.

Investigators will make treatment-based decisions using RECIST 1.1. Adverse events will be monitored throughout the subjects' participation in the trial and graded in severity according to the NCI Common Terminology Criteria for Adverse Events (CTCAE) version 5.0 per protocol [Section 10.1](#).

[figure not shown]
CONFIDENTIAL

This material is the property of the University of Pennsylvania. Do not disclose or use except as authorized in writing by the study sponsor.

The primary objectives of the trial include determination of ORR per RECIST 1.1 for the combination of pembrolizumab and itacitinib and the safety of this combination, as assessed by CTCAE. Pre-specified adverse events of clinical interest include the following events: 1) Grade  $\geq$  3 diarrhea 2) Grade  $\geq$  2 colitis, 3) Grade  $\geq$  2 pneumonitis, 4) Grade  $\geq$  3 hypo- or hyperthyroidism, 5) Grade  $\geq$  2 hypophysitis, 6) Grade  $\geq$  2 uveitis, 7) Grade  $\geq$  2 nephritis, 8) Grade  $\geq$  3 anemia, 9) Grade  $\geq$  3 thrombocytopenia, and 10) Grade  $\geq$  3 neutropenia.

The secondary objective of this trial is to collect paired tumor biopsies and peripheral blood to characterize immune biomarkers of response to treatment with pembrolizumab and itacitinib. Additional secondary objectives include determination of progression free survival, duration of response and overall survival, up to week 16 when the subject reaches end of study.

**Figure 1. Study Schema**

### 3.0 OBJECTIVES

#### 3.1 Primary Objectives & Hypotheses

- 1) To determine the objective response rate at 12 weeks according to RECIST 1.1 for the combination of pembrolizumab and itacitinib among patients with previously untreated, PD-L1 positive metastatic NSCLC. Responses will be compared to the subject's baseline assessment and historical controls using pembrolizumab monotherapy.
- 2) To evaluate toxicities (CTCAE v5.0 scoring) of pembrolizumab and itacitinib in patients with previously untreated, PD-L1 positive metastatic NSCLC

CONFIDENTIAL

This material is the property of the University of Pennsylvania. Do not disclose or use except as authorized in writing by the study sponsor.

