## 4.2 Rationale

### 4.2.1 Rationale for the Trial and Selected Subject Population

The therapeutic benefit of immune checkpoint blockade has now been seen in multiple malignancies, with durable responses observed in a subset of patients [1, 9, 34, 39]. In spite of these exciting results, only a limited number of patients respond to PD-1 blockade, with response rates of approximately 20% in an unselected population. PD-L1 expression is the best-studied predictive biomarker for response to checkpoint blockade in NSCLC [40]. While PD-L1 is an imperfect biomarker, with significant dynamism and heterogeneity, a recent study of patients with tumors expressing a high level of PD-L1 (>50%) pembrolizumab was found to improve overall

CONFIDENTIAL

This material is the property of the University of Pennsylvania. Do not disclose or use except as authorized in writing by the study sponsor.

survival and progression free survival over platinum doublet chemotherapy in the first line treatment of NSCLC [1, 41] Even in this population enriched for patients likely to respond to PD-1 inhibition, the response rate to pembrolizumab was only 44.8%. While this is a great advance, there is clearly room for improvement as we attempt to extend the benefits of anti-PD-1 therapy to a larger patient population.

Patients with newly diagnosed stage IV or metastatic NSCLC with tumor PD-L1 expression greater than or equal to 50% will be enrolled in this study prior to any systemic therapy for metastatic disease. This patient population is selected because 1) PD-L1 is itself upregulated by interferon signaling and could serve as a biomarker for JAK1 inhibition, and 2) we hypothesize that in a proportion of patients with PD-L1+ tumors, feedback inhibition that occurs with prolonged interferon signaling limits response. Thus, patients with high levels of PD-L1 expression may be more likely to benefit from the combination of pembrolizumab and itacitinib.

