### **4.2.3 Rationale for Endpoints**

#### **4.2.3.1 Efficacy Endpoints**

##### **4.2.3.1.1 Primary**

Objective response rate, defined as the percentage of evaluable subjects who achieve a complete or partial clinical response at 12 weeks, according to RECIST 1.1 is the primary endpoint of this study. Given that this is a first line study of a novel combination, ORR was chosen as an earlier indicator of efficacy of the combination and to limit the number of subjects exposed if improved efficacy is not observed. Moreover, based on the mechanism of action, JAK1 inhibition would be predicted to improve the response rate in a population of patients with PD-L1 positive tumors by reducing the expression of additional immune inhibitory pathways in the tumor microenvironment. Responses will be compared to the subject's baseline assessment and historical controls using pembrolizumab monotherapy.

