##### **Objective response rate**

Objective response rate (ORR) is defined as the percentage of evaluable subjects who achieve a complete or partial clinical response according to RECIST criteria

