### **8.2.2 Analysis Populations**

#### **8.2.2.1 Efficacy Analysis Populations**

Subjects who either experience documented progressive disease during the first 12 weeks of treatment or complete the first 12 weeks of treatment and undergo re-staging are considered evaluable for objective response evaluation. Subjects who are withdrawn from study (due to toxicity or other reasons) in the first 12 weeks of treatment and who do not undergo re-staging will be considered unevaluable for objective response evaluation but will be included in the safety analyses. The All Patients as Treated population will be used for estimation of PFS and OS.

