### **8.2.3 Statistical Methods**

#### Primary Objectives

1. Based on evaluable subjects, the objective response rate and 95% confidence interval will be calculated.
2. Toxicities will be graded, categorized and tabled. Toxicity tables will be separately constructed for cycles with pembrolizumab alone (cycles 1-2 and cycle  $\geq 5$ ) or pembrolizumab and itacitinib (cycles 3-4).

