### **8.3 Sample Size**

The required sample size ranges from 11 to 48 evaluable subjects. In the event that 5% of subjects are not evaluable for objective response evaluation, the maximum sample size is 50 subjects.

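### Does the promised comparison with historical pembrolizumab controls need a written reading rule before the response rate can be interpreted?

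*Combined protocol and SAP*

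**What the plan says.** Sections 3.1 and 4.2.3.1.1 carry the same sentence under the primary response objective: "Responses will be compared to the subject's baseline assessment and historical controls using pembrolizumab monotherapy". Section 4.2.3.1.1 counts evaluable subjects who "achieve a complete or partial clinical response at 12 weeks". The definition in 8.2.1 is "the percentage of evaluable subjects who achieve a complete or partial clinical response according to RECIST criteria", with no time point. Section 8.2.3 gives the whole planned analysis: "Based on evaluable subjects, the objective response rate and 95% confidence interval will be calculated".

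Sections 2.1 and 8.1 give the pembrolizumab ORR as 45% (95% CI 37-53%), with its source; 4.2.1 gives the same rate unrounded ("the response rate to pembrolizumab was only 44.8"%). Around that figure 2.1, 5.9 and 8.1 set a null of 35%, described as inferior to pembrolizumab, and an alternative of 55%, described as superior. The trial stops at 2 or fewer of 11 or at 12 or fewer of 30, and recommends further study at 21 or more of 48.

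Under 8.2.2.1, subjects withdrawn in the first 12 weeks without re-staging "will be considered unevaluable for objective response evaluation but will be included in the safety analyses"; 2.1 and 5.8 have them replaced. Section 8.3 allows for this: "In the event that 5% of subjects are not evaluable for objective response evaluation, the maximum sample size is 50 subjects".

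**The concern.** The trial has one arm. Response is measured from a scan taken before any pembrolizumab, and itacitinib starts only at Cycle 3, so change from baseline mixes the two drugs. The historical comparison is then the only planned efficacy comparison that bears on what itacitinib adds. It sits in a primary objective of an open-label study, yet 8.2.3 names no comparator, does not say when or in whom the 45% was measured, and gives no rule for reading the result.

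The 21/48 rule does not do this job. It is calibrated against 35%, and 21/48 is 43.8%, below the quoted rate. If the reading were chosen after the count is known, the same result, say 25 of 48, could be written up as above pembrolizumab or as not distinguishable from it.

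**Working it through.** **1. The plan's own figures.** Let X1, X2 and X3 be binomial with sizes 11, 19 and 18 and response probability p (stage totals 11, 30 and 48, from 8.1).

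- Early stop = P(X1 ≤ 2) + P(X1 ≥ 3 and X1+X2 ≤ 12)
- Go = P(X1 ≥ 3, X1+X2 ≥ 13 and X1+X2+X3 ≥ 21)

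| True ORR | Early stop | Go | Plan states |
|---|---|---|---|
| 35% | 0.7857 | 0.0997 | 0.786 and 0.100 |
| 45% | 0.3698 | 0.5269 | not stated |
| 55% | 0.0783 | 0.9057 | power 0.906 |

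All three stated figures reproduce. The go probability of 0.53 at a true 45% follows from placing the hypotheses 10 points either side of the quoted rate.

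**2. Where a threshold for better than pembrolizumab could lie.** Inputs: 48 evaluable subjects; benchmark 45% (37-53%); exact (Clopper-Pearson) 95% intervals.

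- Point estimate above 45%: 22/48 = 45.8%.
- Interval excludes a fixed 45%: 29/48 = 60.4%, interval 45.3-74.2%; 28/48 has lower limit 43.2%. Wilson (46.3% at 29, 44.3% at 28) and Wald (46.6% and 44.4%) also give 29.
- Benchmark uncertainty carried: the interval's half-width of 0.08 implies about 0.45 × 0.55 × (1.96/0.08)² ≈ 149 historical patients (inferred, not stated). Against 67/149, 29/48 gives two-sided p = 0.063 (z) or 0.070 (Fisher); 30/48 gives 0.035 or 0.046. The threshold is 30, and stays there for 140 to 160 historical patients.
- Interval excludes 53%: 33/48, lower limit 53.75%; 32/48 gives 51.6%. With Wald, 32 is enough.

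These are candidate cut-offs, not a range of results; any count above 33 passes them all.

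**3. Chance of reaching each along the three-stage path.**

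| Cut-off | True 45% | True 55% |
|---|---|---|
| 22 | 0.455 | 0.884 |
| 29 | 0.023 | 0.272 |
| 30 | 0.011 | 0.185 |
| 33 | 0.0008 | 0.037 |

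At 29 the chance rises to 0.54 if the true ORR is 60% and 0.79 if it is 65%.

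**4. What the planned output already shows.** 21/48 would appear as 43.8% (29.5-58.8%) and 25/48 as 52.1% (37.2-66.7%). Both intervals contain 45%, which anyone can see by setting them beside the figure in 8.1.

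**5. Time point and denominator.** Week 12 is fixed for this trial in 2.1, 3.1, 4.2.3.1.1, note 11 of the flow chart in 6.1, and 7.1.2.6, so its absence from 8.2.1 is a slip. The time point of the 45% is not given. If a week-12 monotherapy rate were 40% or 37% (assumptions only), the interval-based count would be 27 or 25. For the denominator, 50 − 48 = 2 unevaluable subjects would turn 29/48 into 29/50, with lower limit 43.2%; 30/50 gives 45.2%. The plan's denominator is evaluable subjects, so 29/50 is an additional display and not the defined endpoint.

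**The case for a change.** The strongest case for a change is that a comparison named in a primary objective should not be left to judgement after the data are in. At a true 45%, calling the regimen better at 22 responders would be wrong with probability 0.455, against 0.023 at 29: a twenty-fold spread decided by an unwritten choice. A few sentences in 8.2.3 would settle it without touching the sample size or the cut-offs.

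Part of that stands. Section 8.2.3 does not tie the 45% to the promised comparison, and no section says when or in which patients that rate was measured.

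The rest does not. The spread belongs to a claim of superiority that the plan nowhere promises. A bare point-estimate win and clearing the benchmark's upper limit are readings brought in from outside. The analysis actually planned, a 95% interval, points to 29 against a fixed 45%, or 30 once the benchmark's uncertainty is counted. Writing in 29/48 would treat 45% as exact, and would yield the favourable wording only about one time in four at the rate the trial is designed to detect. The missing details of the benchmark would still have to come from its source, so new wording here could not supply them. Finally, a subject with no re-staging contributes no response, so the ORR among all treated subjects follows from counts the trial will hold in any case.

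**Conclusion.** No change follows. The missing reading rule is a gap that an analyst fills sensibly, by reporting the week-12 ORR and its 95% interval beside 45% (37-53%) as a description. Followed exactly, the plan gives a valid estimate and interval and a correctly calibrated decision whose conclusion goes no further than more study. A fixed threshold of 29 or 30 of 48 would be a fair choice but not a correction: it alters no stopping boundary, error rate or go decision, and has probability 0.27 or 0.18 at the 55% target. The lack of a time point in 8.2.1 is clerical, since five other places give week 12.

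This rests on two assumptions: that the comparison is reported as descriptive, and that reaching 21/48 is not presented as evidence of benefit over pembrolizumab alone, which the plan does not claim. The figure of 30 also assumes roughly 140 to 160 historical patients, inferred from the quoted interval.

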### **3.2 Secondary Objectives**

- 1) To collect paired blood and tumor tissue samples in order to perform mechanistic studies on treatment-related changes in the subject and tumor immune profiles
- 2) To determine the median progression free survival (PFS) and duration of response (DOR) at week 12 as well as overall survival (OS) for subjects treated with pembrolizumab and itacitinib, up week 16.

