### **3.3 Exploratory Objectives**

- 1) To perform analyses of tumor infiltrating lymphocytes (TILs) to identify changes in functional markers in response to the addition of itacitinib to pembrolizumab.
- 2) To perform gene expression studies of tumor tissue using Nanostring to characterize genetic effects in response to immunotherapy.

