#### **4.2.3.2 *Exploratory objectives***

Perform analyses of tumor infiltrating lymphocytes (TILs) to identify changes in functional markers in response to the addition of itacitinib to pembrolizumab. This study will be a pilot feasibility study of performing multiparametric analysis of TILs, particularly CD8+ T cells, from patients with metastatic NSCLC using approaches such as flow cytometry and multicolor immunohistochemistry.

Given the potential role for chronic interferon signaling as well as other inflammatory cytokines regulated by JAK/STAT signaling in impairing T cell function, we anticipate that response to itacitinib and pembrolizumab will be associated with 1) sustained activation of PD1+ T cells after an initial proliferative burst as measured by Ki67, 2) high pre-treatment interferon levels that is suppressed during treatment, and 3) high gene expression levels of resistance-associated ISGs. We hypothesize that subjects failing to respond to treatment will show initial proliferative burst in PD1+ T cells that is not sustained despite continued pembrolizumab, and 2) decreased expression of various other markers of T cell activation.

Additionally, deep sequencing of the T cell receptor (TCR) in tumor and blood will be performed as feasible to identify clones that expand after treatment and monitor their persistence over time. These are non-biased approaches to identify tumor reactive T cells in subjects where the specific neoantigen is not known.

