### 5.3.2 Timing of Dose Administration

Trial treatment should be administered on Day 1 of each cycle after all procedures/assessments have been completed as detailed on the Trial Flow Chart ([Section 6.0](#)). Trial treatment may be

CONFIDENTIAL

This material is the property of the University of Pennsylvania. Do not disclose or use except as authorized in writing by the study sponsor.

administered up to 3 days before or after the scheduled Day 1 of each cycle due to administrative reasons.

All trial treatments will be administered on an outpatient basis.

Pembrolizumab will be administered q3 weeks as a 30 minute IV infusion. Up to 4 cycles of pembrolizumab will be administered as part of this study. If the PI considers it beneficial for the subject, a fifth cycle may be administered prior to EOS visit. Pembrolizumab treatment cycle intervals may be increased due to toxicity as per package insert. Sites should make every effort to target infusion timing to be as close to 30 minutes as possible. However, given the variability of infusion pumps, a window of +/- 10 minutes is permitted.

Itacitinib will be administered daily starting at Cycle 3/Day 1 and continue for a total of 6 weeks (42 days). Itacitinib should be taken orally by the subject at the prescribed dose- 200 mg QD (2 x 100 mg tablets). If dose reductions are required due to toxicity, the prescribed dose may be reduced to 100 mg QD (1 x 100 mg tablet). Itacitinib should be taken with water, and may be taken without regard to food. If itacitinib doses are missed due to toxicity (per [Table 3](#)) or if vomiting occurs, these missed doses will not be made up.

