#### **Hypotheses**

- Pembrolizumab and itacitinib will be associated with an ORR of at least 55% among patients with previously untreated, PD-L1 positive metastatic NSCLC.
- Pembrolizumab and itacitinib will be well tolerated among patients with previously untreated, PD-L1 positive metastatic NSCLC.
- The addition of itacitinib to pembrolizumab will result in increased T cell activation in the peripheral blood and decreased interferon signaling in tumor tissue in the week 12 biopsy, compared to the week 6 biopsy.

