#### Secondary Objectives

1. Changes in immune pharmacodynamic biomarkers will be examined with scatter plots and summary statistics. Fold changes from baseline values will be estimated and summarized.
2. Duration of response, progression-free survival and overall survival will be estimated by the method of Kaplan and Meier. Median values and 95% confidence intervals will be calculated.

CONFIDENTIAL

This material is the property of the University of Pennsylvania. Do not disclose or use except as authorized in writing by the study sponsor.

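### Marker changes are credited to adding itacitinib, but the only named estimate mixes in pembrolizumab's own time course, and the run-in draws allow only a partial check

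*Combined protocol and SAP*

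**What the plan says.** **Design.** Section 1.0: "This is a single center, single arm phase 2 study to establish the safety and efficacy of itacitinib". Section 2.1: "Subjects will receive 2 cycles of pembrolizumab (200mg every 3 weeks), and then undergo repeat imaging and tumor biopsy". Itacitinib then starts on Cycle 3 Day 1 in every subject and runs for six weeks, with pembrolizumab unchanged.

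**Claims.** Section 3.2 sets the collection objective, "To collect paired blood and tumor tissue samples in order to perform mechanistic studies on treatment-related changes in the subject and tumor immune profiles". Section 3.3 plans analyses of tumor-infiltrating lymphocytes "to identify changes in functional markers in response to the addition of itacitinib to pembrolizumab". The third hypothesis in 8.2.1 is causal in wording: "The addition of itacitinib to pembrolizumab will result in increased T cell activation in the peripheral blood". It also predicts lower interferon signaling in tumor and sets the week 12 biopsy against the week 6 biopsy. Whether week 6 is also the reference for blood is not stated.

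**Analysis.** Sections 8.2 and 8.2.3 plan scatter plots and summary statistics, then: "Fold changes from baseline values will be estimated and summarized". Baseline is not defined for markers, and no contrast between the periods before and after itacitinib is named. For toxicity, the same section does split pembrolizumab-alone cycles from cycles 3-4.

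**Expected course.** Section 4.2.3.2 expects, in non-responders, an early burst of T-cell proliferation "that is not sustained despite continued pembrolizumab".

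**Samples.** The flow chart (6.1) marks research blood at Screening, Cycles 1 to 4 and Week 12. Section 5.3.2 adds: "Trial treatment should be administered on Day 1 of each cycle after all procedures/assessments have been completed". Tumor is biopsied twice, after Cycle 2 and at the end of Cycle 4. Archived tissue is optional.

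**The concern.** Itacitinib exposure coincides with time after week 6 in every subject, and there is no concurrent pembrolizumab-alone group. Any change in a marker after week 6 could come from itacitinib, from continuing pembrolizumab, or from both.

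The choice of reference decides how much of pembrolizumab's course enters the estimate. If baseline means pre-treatment, the fold change at week 12 carries all 12 weeks of it. If the reference is week 6, the first six weeks drop out but any later drift remains. The protocol's own biology gives reason to expect movement: a burst that fades raises an estimate taken from pre-treatment and lowers one taken from week 6.

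At stake is the mechanistic conclusion. The blood result could show an increase when itacitinib does nothing, or a decrease when it works, and hypothesis 3 invites the reader to call either one an effect of the added drug.

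**Working it through.** **The plan's own figure.** None is given for biomarkers. The only design calculation concerns response rate, and its figures reproduce (0.0997, 0.9057 and 0.7857 against the stated 0.100, 0.906 and 0.786). They have no bearing on this point.

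**Inputs.** From the documents: one arm; itacitinib from Cycle 3 Day 1 (week 6); blood marks at Screening, Cycle 1, weeks 3, 6 and 9, and week 12. Assumed, because the documents give none of it: n = 40 with paired draws; within-subject SD 0.4 natural-log units per draw (range 0.3 to 0.5); independent errors; the marker courses below.

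**Formulas.**
- Ratio of two draws: SE = SD x sqrt(2/n) = 0.4 x sqrt(2/40) = 0.0894.
- Run-in-adjusted contrast, (log C4 - log C3) - (log C3 - log C2): the weights are 1, -2, 1, so SE = SD x sqrt(6/n) = 0.4 x sqrt(6/40) = 0.1549. Its ratio is C4 x C2 / C3².
- Probability that the 95% CI lies above 1 = 1 - Φ(1.96 - ln ratio / SE). Below 1, it is Φ(-1.96 - ln ratio / SE).

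**Step 1: the two simple ratios.** Assume pembrolizumab alone gives 3.0, 2.0, 1.5 and 1.2 times baseline at weeks 3, 6, 9 and 12.
- No itacitinib effect, week 12 over baseline: 1.20. ln 1.20 / 0.0894 = 2.04, so the CI lies above 1 in 53% of trials (78% at SD 0.3, 37% at SD 0.5).
- True 1.4-fold effect, week 12 over week 6: 1.4 x 1.2 / 2.0 = 0.84. ln 0.84 / 0.0894 = -1.95, so the CI lies below 1 in 50% (74% at SD 0.3, 34% at SD 0.5).

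More generally, a natural fall of 20% to 50% between weeks 6 and 12 cancels a true increase of 1/0.8 = 1.25-fold to 1/0.5 = 2.0-fold.

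**Step 2: the week 6 reference at the planned stage sizes.** Assume the SD of the paired log2 change is 1 and itacitinib does nothing. A 1.25-fold drift after week 6 makes a 95% t-interval exclude no change with probability 0.16 at n = 11, 0.40 at n = 30 and 0.59 at n = 48, against a nominal 0.05.

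**Step 3: can the run-in draws remove the mixing?** Apply the adjusted contrast with no itacitinib effect (n = 40, SD 0.4), where the right answer is 1.00:

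| Assumed course, weeks 3 / 6 / 9 / 12 | Contrast | 95% CI excludes 1 | Week 12 / week 6 |
|---|---|---|---|
| 3.0 / 2.0 / 1.5 / 1.2 | 1.125 | above in 12% | 0.60 |
| 3.0 / 1.5 / 1.3 / 1.2 (faster fade) | 1.73 | above in 94% | 0.80 |
| 1.5 / 2.0 / 2.0 / 2.0 (plateau) | 0.75 | below in 46% | 1.00 |
| 1.5 / 2.0 / 1.5 / 1.2 (peak at week 6) | 0.56 | below in 96% | 0.60 |

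The nominal rate is 2.5% per side. Under the plateau with a true 1.4-fold effect, the contrast detects it in 5% of trials and the simple ratio in 96%. A straight line through weeks 0, 3 and 6 is no safer: it is unbiased only if the course is linear, and it raises the SE about 1.71-fold over a week-12/week-6 difference.

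**The case against.** The SAP never says that fold change from baseline is the itacitinib effect. It also plans scatter plots and summary statistics, and hypothesis 3 already names week 6 as the biopsy reference. Objective 3.2 concerns treatment-related change, for which fold change from pre-treatment is a fair description of the whole regimen. These are descriptive secondary and exploratory analyses. No biomarker test or interval is planned, and the efficacy decision rests on response rate. All of this stands. It means that the 53% in Step 1 belongs to one possible reading of an undefined baseline, and that the CI rates describe an inference the SAP does not itself plan. It does not supply the missing definition, and hypothesis 3 remains worded as cause and effect.

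The draw times are also less certain than the flow chart suggests. Its footnote sends collection details to a laboratory manual outside these documents. Section 5.3.2 makes a pre-dose Cycle 3 draw likely, not certain.

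A reader might infer that the run-in draws are an internal control that isolates itacitinib, so that the adjusted contrast should become the main estimate. The documents do not support this. Only weeks 3 and 6 reflect pembrolizumab alone after treatment starts, and the week 6 to 12 course without itacitinib is never observed. As Step 3 shows, the contrast can be wrong in either direction, and under a plateau it is worse than the simple ratio.

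**Conclusion.** The point holds in a limited form. Hypothesis 3 attributes marker changes to adding itacitinib, while the only named estimate is fold change from an undefined baseline in a single arm with pembrolizumab ongoing. Pre-treatment as the reference mixes in the whole 12-week course. Week 6 as the reference leaves only the drift after week 6, which nothing in the trial measures. The run-in blood supports a sensitivity check that depends on an assumed trend, and no more. For tumor, with two on-treatment biopsies and optional archived tissue, even that check is unavailable.

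The structural argument rests on the documents. Every magnitude above is an illustration under assumed courses, SD and n. The response-rate decision is unaffected; what changes is what the trial can say about mechanism. It is worth correcting because mechanism is a stated aim and the correction is cheap.

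**What to change.** In 8.2.3:

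1. Define baseline for each comparison. For blood and serum markers, make the pre-dose Cycle 3 Day 1 draw the reference for the itacitinib question, and state that it is taken before the first itacitinib dose.
2. Report side by side, on the log scale with 95% CIs, the run-in change (baseline to Cycle 3) and the combination-period change (Cycle 3 to Cycle 4 and to Week 12).
3. Keep fold change from pre-treatment as a description of the whole regimen.
4. If a run-in-adjusted contrast is added, such as (log C4 - log C3) - (log C3 - log C2), label it a sensitivity analysis. State that it assumes the run-in trend continues, and that it can be biased either way if the early burst fades or levels off.
5. Describe blood results, and the tumor difference from week 6 to week 12, as changes during the combination period, not as the effect of itacitinib. Align the wording of hypothesis 3 with this.

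The cost is SAP wording, a little more analysis of samples already scheduled, and a weaker causal statement.
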